7.5 Adjustments for Multiple Comparisons

No adjustments will be made.

7.6 Demographic and Other Baseline Characteristics

Patient demographics, medical history, aneurism symptoms, and baseline neurological status will be summarized using descriptive statistics for continuous variables (mean, standard deviation, number of observations, minimum and maximum) and frequency tables for discrete variables.

Baseline Demographic and Risk Factors

Data will be summarized and reported in a table entitled Summary of Patient Demographics (ITT population); A similar table will be restricted to the ICA population. This table summarizes the patient population with respect to age at entry into the study, gender and risk factors. Age will be reported in years. Age will be summarized using descriptive statistics: n, arithmetic mean, standard deviation, median, and range (i.e., minimum and maximum values). Age will also be presented in mutually-

[REDACTED]

Results will be summarized by type using counts and percentages.

The type of imaging modality will be summarized using counts and percentages.

[REDACTED]

If there are multiple types of imaging used for a patient, the image with the highest quality and used in the independent core lab read will be reported.

The type of aneurysm will be summarized using counts and percentages (per Core Lab).

[REDACTED]

Determining the side and location of the Internal Carotid Artery, Vertebral Artery, Anterior Cerebral Artery, and Middle Cerebral Artery will be summarized using counts and percentages (per Core Lab). Precise parent artery location will be summarized using counts and percentages (per Core Lab). Continuous variable measurements for Aneurysm maximal diameter (mm), Aneurysm dome (mm), Aneurysm neck length (mm), Dome/neck ratio, Parent artery diameter distal to the target aneurysm (mm) and Parent artery diameter proximal to target aneurysm (mm) will be summarized using

For this clinical investigation, only those pre-existing conditions that are currently on-going on the date of the study procedure were recorded. Data will be summarized and reported in a table entitled Summary of Medical History (ITT population) per SOC and MedDRA coding conventions; a similar table will be restricted to the ICA population.

Neurological Assessments at Baseline

Subjects may undergo (as indicated by site per standard of care) a neurologic examination and assessment using the mRS and NIHSS at baseline and also prior to the procedure. Data will be summarized and reported in a table entitled Summary of Neurological Assessments at Baseline (ITT population); a similar table will be restricted to the ICA population. The summary will include the baseline results for the mRS (Baseline) and NIHSS (recorded pre-procedure). The mRS, results will be presented using counts and percentages for each mRS score. For the NIHSS, results will be summarized using descriptive statistics as observed.

A NIHSS table will be presented in a listing format entitled NIH Stroke Scale (NIHSS) Scores will contain the baseline pre-procedure and post-procedure scores by patient, as well as the date and time the score was recorded. This listing will be sorted by patient number. As the screening/baseline assessments may be performed prior to the procedure at Day 0 some subjects will have only a single value for NIHSS. In this case the screening/baseline value will be left blank in the listing. A listing entitled Modified Rankin Scale (mRS) Scores will contain the pre-procedure and post-procedure scores by patient and date the score was recorded. This listing will be sorted by patient number.

Platelet Reactivity Test Results

Data will be summarized and reported in a table entitled Summary of the Platelet Reactivity Test Results Recorded at Baseline (ITT population); a similar table will be restricted to the ICA population. The last results prior to the procedure will be reported for each patient. The platelet test results will be summarized using descriptive statistics: n, arithmetic mean, standard deviation, median, range (i.e., minimum and maximum values). Subjects with missing data that cannot be resolved prior to database lock will not be included in the tabulation and excluded from the summary statistics; all data will be presented in a listing. A summary of the platelet reactivity data recorded after the procedure will be presented in a table entitled Summary of Post-Procedure Platelet Reactivity Test Data; a similar table will be restricted to the ICA population. The supportive data for Table platelet reactivity will be presented in a listing format entitled Platelet Reactivity Test Results. This listing will be sorted by patient number. The individual elements to be presented from the CRF are presented below.

[Redacted content]

[REDACTED]

[REDACTED]

[REDACTED]

[REDACTED]

[REDACTED]

7.7 Treatment Characteristics

Procedure characteristics, study device usage and procedure imaging information will be summarized using descriptive statistics for continuous variables (mean, median, standard deviation, number of observations, minimum and maximum) and frequency tables for discrete variables.

Pipeline™ device STUDY PROCEDURE with Shield Technology™ and Efficacy

This section will discuss the tabulation and analysis of the study procedure, type and size of the Pipeline™ device with Shield Technology™ and follow-up. Detailed descriptions of the statistical procedures that will be used to analyze the study variables will be described below.

In the design of the outcome data from this registry, a collective approach has been used to compile the results within an overall summary table. Given there is clinical interest to examine multiple variables for the various populations, this approach has been adopted. Separate subset tables may be extracted for discussion for the overall summary table.

Study Procedural Characteristics

The summarization of the procedural data for the ITT population will be presented in a table entitled Summary of the Primary Study Procedure Characteristics; a similar table will be restricted to the ICA population. The term Primary Study Procedure refers to the initial procedure, given the patient may require re-treatment.

Time of skin incision to time of first Pipeline™ device with Shield Technology™ introduction will be calculated and presented in minutes. The time of first Pipeline™ device with Shield Technology™ introduction to last Pipeline™ device with Shield Technology™ delivery system removal will be calculated and presented in minutes. Time of skin incision to time of skin closure will be calculated and presented in minutes. Cumulative flouro time will be summarized for the ITT population in minutes. The time interval data described above will be summarized using descriptive statistics: n, arithmetic mean, standard deviation, median, range (i.e., minimum and maximum values). Subjects with missing data that cannot be resolved prior to database lock will not be included in the tabulation and excluded from the summary statistics; all data will be presented in a listing.

The information collected and to be summarized and reported in the listings is presented below:

[REDACTED]

[REDACTED]

- [REDACTED]
- [REDACTED]

[REDACTED]

[REDACTED]

[REDACTED]

[REDACTED]

[REDACTED]

[REDACTED]

[REDACTED]

- [REDACTED]
- [REDACTED]
- [REDACTED]
- [REDACTED]

[REDACTED]

[REDACTED]

- [REDACTED]
- [REDACTED]

Pipeline™ Device with Shield Technology™ Deployment

A summary of the use of the Pipeline™ devices for the ITT population will be presented in a table entitled *Summary of Pipeline™ Device Deployment*; a similar table will be restricted to the ICA population. The number of Pipeline™ devices used and the reasons for multiple device use for the primary study procedure will be presented. The count and percentage for the following categories applicable to the SHIELD device will be summarized:

[REDACTED]

[REDACTED]

[REDACTED]

[REDACTED]

[REDACTED]

[REDACTED]

- [REDACTED]
- [REDACTED]

[REDACTED]

- [REDACTED]
- [REDACTED]
- [REDACTED]
- [REDACTED]
- [REDACTED]

Side branches covered by PFED?

- [REDACTED]
- [REDACTED]
- [REDACTED]
- [REDACTED]
- [REDACTED]
- [REDACTED]
- [REDACTED]
- [REDACTED]
- [REDACTED]
- [REDACTED]
- [REDACTED]
- [REDACTED]
- [REDACTED]
- [REDACTED]
- [REDACTED]
- [REDACTED]
- [REDACTED]
- [REDACTED]
- [REDACTED]
- [REDACTED]
- [REDACTED]
- [REDACTED]
- [REDACTED]
- [REDACTED]
- [REDACTED]
- [REDACTED]
- [REDACTED]
- [REDACTED]
- [REDACTED]
- [REDACTED]
- [REDACTED]
- [REDACTED]
- [REDACTED]
- [REDACTED]
- [REDACTED]
- [REDACTED]
- [REDACTED]
- [REDACTED]
- [REDACTED]

- [REDACTED]
- [REDACTED]
- [REDACTED]
- [REDACTED]
- [REDACTED]
- [REDACTED]
- [REDACTED]
- [REDACTED]

The supportive data for ancillary devices table will be presented in a listing entitled *Ancillary Devices*. This listing will be sorted by patient number. The list of study devices will be presented in a listing entitled *Pipeline™ device with Shield Technology™ Accountability*.

Overall Summary of Device and Peri-Procedure Variables

The overall summary of the results (site reported when Core Lab adjudicated data not available) from the study procedure will be summarized in a table entitled *Overall Summary of the Device and Peri-Procedure Variables*; a similar table will be restricted to the ICA population. Within this table, 9 separate parameters will be summarized:

- Successful deployment of the study device to the target site. Successful deployment has a binary outcome and comes directly from the clinical case report form.
- Implantation of the study device. The determination of implantation has a binary outcome and comes directly from the clinical case report form.
- Number of times re-sheathing was attempted. The count (0, 1, 2, or >2) comes directly from the clinical case report form.
- Entire IA neck covered by the study device. Complete neck coverage has a binary outcome and comes directly from the core lab
- Side branches covered by the study device. Complete side branch coverage has a binary outcome and comes directly from the core lab
- Post-deployment stasis (complete, significant, or no disruption of inflow jet); evaluated as 1 of 3 possible states, comes directly from the core lab
- Target aneurysm partially thrombosed; a binary endpoint that comes directly from the core lab
- Percentage of target aneurysm thrombosis; a continuous endpoint that comes directly from the core lab
- Achievement of wall apposition; a binary endpoint that comes directly from the core lab.

The duration of the procedure (min) will also be summarized and presented using descriptive statistics.

The supportive data for these series of tables will be presented in a listing entitled *Device and Peri-Procedure Analyses*. This listing will be sorted by patient number.

Overall Summary of the Post-Procedure Variables Recorded Over Time

The post-procedure analyses will be summarized for the following 5 time points: Post-Procedure Discharge, 1 Month Post-Procedure, 3 Months Post-Procedure, 6 Months Post-Procedure, and 1 Year Post-Procedure. The following 10 separate parameters will be summarized:

- Aneurysm occlusion (Class 1: Complete obliteration, Class 2: Residual neck, or Class 3: Residual Aneurysm), derived from the post-procedure imaging adjudicated by core lab.
- Modified Rankin Scale (mRS). The mRS score at 1 year will be dichotomized (>2 vs. ≤ 2) and summarized using counts, percentages, and 2-sided 95% exact binomial confidence intervals.
- NIH Stroke Scale (NIHSS)
- Platelet reactivity testing
- Change in antiplatelet therapy because of the platelet reactivity testing
- Retreatment of the target aneurysm
- Major stroke in the territory supplied by the treated artery or neurological death at 30 days post-procedure due to procedural complications
- Intracerebral hemorrhage (ICH) > 30 days post-procedure (Delayed ICH)
- Parent artery stenosis (per Core Lab)
- Device migration (per Core Lab)

The incidence of complete aneurysm occlusion without significant parent artery stenosis ($\leq 50\%$) at 1 year post-procedure and without re-treatment of the target aneurysm (Primary Efficacy Endpoint) will be based on the Scale of Roy. Results will be based on the ITT population and will include the target aneurysm for each patient. The target aneurysm is defined as the largest aneurysm treated in the study procedure as identified by the core laboratory.

Results based on the ITT population will be presented in a table entitled *Overall Summary of the Post-Procedure Variables by Time*. The table will contain the point estimate and the confidence limit based on the exact Clopper-Pearson method. The supportive data for this table will be presented in a listing entitled *Post-Procedure Variables*. This listing will be sorted by patient number. Results based on the ICA population will be presented in a similar table and results based on the FAS population will be presented in a similar table.

Concomitant Medications

Concomitant medications refer to all medications taken from Day 0 thru study exit. *Antiplatelet medications were collected per their actual start date even if these were started prior to the study treatment (Day 0)*. *Prior medications* refer to all medications that were started and stopped prior to the first treatment with the Pipeline™ device with Shield Technology™ and will not be reported as concomitant.

The count and percent of subjects on anti-platelet medications will be summarized for 7 days pre-procedure, as well as for post procedure (were available) and presented in tables entitled *Summary of Dual Antiplatelet Therapy (DAPT)*. A summary of the concomitant medications will be presented in a table entitled *Summary of Concomitant Medications*, containing a clear declaration regarding the start date of the medication relative to the study procedure. The concomitant medications taken by the ITT population will be displayed in a listing entitled *Concomitant Medications*.

7.8 Interim Analyses

None

7.9 Evaluation of Objectives

As previously described, the primary objective of this study is to assess the *outcomes* of the Pipeline™ Flex Embolization Device with Shield Technology™ in patients undergoing treatment for intracranial aneurysms in a large real-world, post-market setting. *Outcomes* will be assessed based on a series of standardized measurements recorded during the procedure and during the post-procedure follow-up period.

The Intent to Treat (ITT) will be considered the primary population, but not limited to, in the analysis of data for this study. When analyzing an outcome within a population, missing data will be reflected as the function of the denominator reported (xx.x% n/N) while the population number will remain constant. [i.e. ITT n=200 outcome Y (50%, 98/196)]

The pre-specified study endpoints and analysis listed here are the primary body of data that will be collected, analyzed, and summarized in a series of tables, lists, and graphs as part of the final report for this study. Other analysis will be conducted as part of the final report but these are the core set of analyses that will constitute the foundation of the clinical study report.

Primary endpoints:

Safety:

- Occurrence of major stroke in the territory supplied by the treated artery or neurological death post-procedure (1-year)

Effectiveness:

- Complete aneurysm occlusion (defined as Raymond-Roy grade 1) without significant parent artery stenosis ($\leq 50\%$) or retreatment of the target aneurysm post-procedure (1-year)

Secondary endpoints:

Safety:

- Occurrence of major stroke in the territory supplied by the treated artery or neurological death at 30 days post-procedure due to procedural complications
- Delayed intracerebral hemorrhage > 30 days post-procedure

Effectiveness:

- Device deployment success rate at the target site

Analysis for primary effectiveness endpoint interaction of site homogeneity and poolability testing will be conducted and reported.

Analysis of primary effectiveness endpoint by:

- Missing Data by Worst Case Scenario
- Aneurysm Location (with observed data)
- Aneurysm Location by Artery Segments (ITT population with observed data)
- By age (ITT and FAS population with observed data)

Analysis for primary effectiveness endpoint tipping point for incidence of complete target aneurysm occlusion at 1 year post procedure (ITT population)

CEC event of interest through 1 year will be reported for:

- GUSTO Bleeding
- Procedural:
 - Access Site Complications
 - Procedural Systemic Complications
 - Vasospasms
- Neurological Events:
 - Focal Neurological Deficit
 - Cerebral Infraction
 - Transient Ischemic Attack (TIA)
 - Intracranial Hemorrhage (ICH)
 - Stroke
 - Death

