9.4 Analysis of Baseline Demographics and Procedural Characteristics

Descriptive statistics will be generated for pre-intervention demographics, aneurysm characteristics and procedural characteristics, device usage and adverse events. Categorical variables will be analyzed using frequency, incidence, and event rate. For continuous variables collected in the study, analysis will include mean, median, standard deviation, and range.

The following data points will be analyzed in this study:

- Antiplatelet therapy regimen
- Adverse events related to antiplatelet therapy
- Platelet reactivity testing results
- Moderate and Severe bleeding events utilizing GUSTO criteria
- All intracranial hemorrhages and delayed intracranial hemorrhages (>30 days post-procedure)
- Index procedure time
- Number of Pipeline™ Flex Embolization Device with Shield Technology™ utilized
- Device deployment success rate at target site
- Aneurysm occlusion at 6 months, 1 year and at last follow-up
- Recurrence and retreatment rates at 1 year post-procedure and at last follow-up

- The composite percentage of patients with modified Rankin Scale of 0-2 or no change from baseline at 1 year and at last follow-up.
- Occurrence of major stroke in the territory supplied by the treated artery or neurological death.

Major Stroke events will be further characterized based on whether:

- Event was caused by thromboembolic events
- Event was caused by side-branch occlusion due to the study device

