mRS	Modified Rankin Score	Scale for measuring general neurological function. 0 No symptoms at all 1 No significant disability despite symptoms; able to carry out all usual duties and activities 2 Slight disability; unable to carry out all previous activities, but able to look after own affairs without assistance 3 Moderate disability; requiring some help, but able to walk without assistance 4 Moderately severe disability; unable to walk without assistance and unable to attend to own bodily needs without assistance 5 Severe disability; bedridden, incontinent and requiring constant nursing care and attention 6 Dead
NIHSS	National Institute of Health Stroke Scale	Method for quantifying neurologic deficits developed by the National Institutes of Health. It is used to assess the severity of a stroke.
PED	Pipeline Endovascular Device	Pipeline Endovascular Device

Abbreviation	Abbreviated Term	Definition
Primary Efficacy Endpoint	Complete aneurysm occlusion (defined as Raymond-Roy grade 1 ⁵⁵) without significant parent artery stenosis (\leq 50%) or retreatment of the target aneurysm 1-year post-procedure	The primary effectiveness endpoint assessed by: 
• Occlusion status: by a 3-member adjudicated read by the imaging Core Laboratory according to the Scale of Roy• Parent Artery stenosis: by the 3-member adjudicated read by the imaging Core Laboratory.• Retreatment: by the investigator reported events of retreatment.

Abbreviation	Abbreviated Term	Definition

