The patient will be tested at the discretion of the site per standard of care procedures for antiplatelet response and the appropriate dose of antiplatelet agents will be given after the Pipeline™ device with Shield Technology™ placement procedure. Medications could be continued as medically indicated.

Estimated Duration of Patient Participation

Up to 200 subjects will be enrolled over a period of approximately 24 months. The study is intended to have 200 subjects undergo attempted deployment of the Pipeline™ device with Shield Technology™. Each study patient will be followed for 1 year after the primary study procedure. Study participation includes consent, initial screening and baseline, treatment using the Pipeline™ device with Shield Technology™, discharge exam and follow-up visits at approximately 30, 90, 180 days, and 1 year. The total study duration is expected to be approximately 3 years.

Schedule of Assessments

	Baseline	Procedure	Discharge	1 Month	3 Months	6 Months	1 Year	Unscheduled
Schedule		Day 0		±14 days	±30 days	±6 weeks	±8 weeks	
Eligibility	X							
Demographics	X							
Aneurysm Symptoms	X	O	O	O	O	O	O	OR
Medical History		X						
Study Procedure		X						
Procedure Imaging		XR						
Ancillary Devices		X						
Study Device		XR						
Discharge			X					
Follow Up				X	X	X	X	XR
Follow-Up Imaging				OR	OR	OR	OR	OR
NIHSS	O	X		O	O	O	O	OR
mRS	O	X		O	O	O	O	OR
Exit			X					

Retreatment Study Procedure				OR	OR	OR	OR	OR
Labs	OR	OR	O	O	O	O	O	OR
Device Specific Event		OR	OR	OR	OR	OR	OR	OR
Adverse Event Assessment		OR	OR	OR	OR	OR	OR	OR

Key: Required=X Optional=O Repeatable=R

ANALYSIS POPULATIONS

The following populations will be considered for the analysis of data for this study:

Intent to Treat (ITT)

The Intention to Treat (ITT) population includes all consented subjects in whom deployment of the Pipeline™ device with Shield Technology™ was attempted.

Full Analysis Set (FAS)

The Full Analysis Set (FAS) population is a subset of the ITT population including only those subjects in whom the Pipeline™ device with Shield Technology™ was implanted.

Internal Carotid Artery (ICA) Population

The Intra-Cranial Artery Population (ICA) is a subset of the ITT population including only those subjects in whom the Pipeline™ device with Shield Technology™ was implanted in the ICA (segments C2-C7).

Non-ICA Population

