7.2.2 General Conventions for Summarization

Summary statistics will consist of the number and percentage of responses or counts at each level for categorical variables (e.g. gender). For continuous variables, the sample size (n), mean, median, standard deviation (SD), minimum, and maximum values will be presented.

All mean and median values will be formatted to one more decimal place than the measured value. Standard deviation values will be formatted to two more decimal places than the measured value. Minimum and maximum values will be presented with the same number of decimal places as the measured value.

The number and percentage of responses will be presented in the form XX (XX.X%).

- All summary tables will include the analysis population sample size (i.e., number of subjects).
- Relative Study Day 0 is defined as the day the patient underwent the study procedure. All study days are determined relative to the day the patient underwent the study procedure.
- Baseline values will be defined as those values recorded immediately prior to the study procedure.
- Change from baseline for differences will be calculated as follows:

$$\text{Change} = \text{Post-baseline value} - \text{baseline value}$$

- Missing data may have an impact upon the interpretation of the trial data. The primary presentation of the overall primary endpoint results will be based on the observed data with multiple imputation for missing data using SAS PROC MI. A methodology is also defined in this section for addressing missing dates.
- Date variables will be formatted as DDMMYYYY for presentation; SAS Date9. format.

Data from this study, when applicable will be presented in a listing format. All listings will be sorted by patient number and date, as applicable.

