7.4 Handling of Missing, Unused, and Spurious Data and Dropouts

Handling of dropouts and missing data will depend on their frequency and the nature of the outcome measure.

Subjects with missing data that cannot be resolved prior to database lock may not be included in the tabulation and excluded from the summary statistics if deemed necessary; a listing will be compiled identifying the subjects. The number and percentage of subjects with each characteristic will be presented. The tabulation of subjects across the different characteristics and conditions is independent; multiple subjects can have multiple conditions. Results will be presented based on the number of respondents in each category using counts and percentages.

When calculating rates of Adverse Events, missing and partial dates will be handled as follows. If the entire Adverse Event start date is missing, then the procedure date will be used for the start date. If the month and the day of the month are missing but the year is available, and the year is the same as the year of the procedure then the procedure date will be used for the start date. If the year is greater than the year of the procedure, then January 1st will be used for the month and day of the start date. If the day is missing, but the month and year are available, then the 1st will be used as the day of the start date unless the imputed date would be before the procedure in which case the procedure date will be used for the start date of the Adverse Event.

For baseline categorical variables, "unknown" responses will be counted as not having the characteristic and will be included in the denominator. Missing values will not be counted in rate denominators.

Handling of Missing Start-dates for Interventions

Rules for imputing a full date for interventions with incomplete or missing start-dates are addressed below. In the unusual case that the month portion of an intervention start-date is missing but the day portion is not missing, the day portion of the intervention will be assumed to be missing. Likewise, in the case where the year portion of an intervention start-date is missing but the month and/or day portion is not missing, the month and/or day portion of the intervention start-date will be assumed to be missing. All missing portion(s) of the intervention starting dates will be handled using the same rules:

- In the event that the day portion (and only the day portion) of the intervention start-date is missing:

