7.13.3 Post-Procedure Analyses

The first series of **Post-Procedure** analyses to be summarized will address the outcomes after the procedure. Within this series, there are 9 separate parameters:

- Aneurysm occlusion (Class 1: Complete obliteration, Class 2: Residual neck, or Class 3: Residual Aneurysm), derived from the post-procedure imaging adjudicated by Core Lab.
- Modified Rankin Scale (mRS); a multinomial endpoint that comes directly from the site reported case report form for evaluating the intra-patient over time and the change from baseline. The mRS will be scored for each patient by an evaluator at the clinical site. The mRS is a well-accepted and defined scoring system for measuring the degree of disability or dependence in the daily activities of people who have suffered a stroke using a multinomial ordinal scale:
 - 0 No symptoms at all
 - 1 No significant disability despite symptoms; able to carry out all usual duties and activities
 - 2 Slight disability; unable to carry out all previous activities, but able to look after own affairs without assistance

The mRS score at 1 year will be dichotomized (>2 vs. ≤ 2) and summarized using counts, percentages, and 2-sided 95% exact binomial confidence intervals.

- NIH Stroke Scale (NIHSS); a continuous endpoint that comes directly from the site reported clinical case report form for evaluating the intra-patient over time and the change from baseline. The NIHSS is a 15-item neurologic examination stroke scale used to evaluate the effect of acute cerebral infarction on the levels of consciousness, language, neglect, visual-field loss, extraocular movement, motor strength, ataxia, dysarthria, and sensory loss.
- Platelet reactivity testing, based on the VerifyNow, VASP, MEA, TEG, LTA testing reported as a percentage. A continuous endpoint that comes directly from the site reported clinical case report form.
- Change in antiplatelet therapy because of the platelet reactivity testing; a binary variable and comes directly from the site reported clinical case report form.
- Retreatment of the target aneurysm; a binary variable adjudicated by the imaging core laboratory. The recurrence of the aneurysm will be summarized using the percentage of subjects that experience aneurysm recurrence. Aneurysm recurrence is defined as an aneurysm that achieves complete occlusion at 6 months post-procedure, and then is no

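### No rule scores subjects who die before 1 year as mRS 6, so deaths can drop out of the 1-year mRS >2 rate and make it too low

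*SAP*

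**What the plan says.** **Outcome.** SAP 7.7 (post-procedure variables over time) states: "The mRS score at 1 year will be dichotomized". The split is >2 versus ≤2, with counts, percentages and a two-sided 95% exact interval. SAP 7.13.3 repeats this. Protocol 9.4 lists a related measure: "The composite percentage of patients with modified Rankin Scale of 0-2 or no change from baseline at 1 year and at last follow-up".

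**Source.** SAP 7.13.3 describes mRS as "a multinomial endpoint that comes directly from the site reported case report form", scored by an evaluator at the site. No other source is named.

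**Collection.** The Schedule of Assessments in SAP 5 uses the legend "Key: Required=X Optional=O Repeatable=R". In the mRS row only the procedure is X. The 1-, 3- and 6-month and 1-year visits are O, and unscheduled visits are OR.

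**Missing values.** SAP 7.9 says: "When analyzing an outcome within a population, missing data will be reflected as the function of the denominator reported". The population size is still displayed. SAP 7.4 adds that subjects with unresolved missing data "may not be included in the tabulation and excluded from the summary statistics if deemed necessary". Imputation is tied to the primary endpoints in SAP 7.2.2: "The primary presentation of the overall primary endpoint results will be based on the observed data with multiple imputation for missing data". The worst-case and tipping-point analyses in SAP 7.9 are for primary effectiveness only.

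**Death on the scale.** The mRS definition in SAP 2 ends: "5 Severe disability; bedridden, incontinent and requiring constant nursing care and attention 6 Dead".

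**The concern.** A subject who dies in, say, month 2 has no 1-year visit. The mRS summary is by time point, and the plan has no rule that carries a death forward. Even a 6 entered on an unscheduled form would not, under the written rules, become the 1-year value. The score is then missing at 1 year, and SAP 7.9 takes the subject out of the denominator. The result tends towards a rate among scored survivors, although the SAP's own scale places death in the >2 group.

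The SAP does have such a rule elsewhere. For primary safety, SAP 7.4 counts subjects who withdraw early after a qualifying event as having had the event. mRS has no equivalent, so how deaths are treated would depend on data-entry habit at up to 25 sites. SAP 3 says the results may support a US indication evaluation, and a functional outcome rate should not depend on that.

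**Working it through.** **1. The plan's own figure.** The example in SAP 7.9 is 98/196 = 50.0% in a population of 200. So 200 − 196 = 4 subjects left the denominator; with all 200 kept it would be 98/200 = 49.0%. This confirms how the rule works.

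**2. Direction.** Let n survivors be scored, b of them with mRS >2, and let d subjects have died.

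- Deaths dropped: b/n
- Deaths scored 6: (b + d)/(n + d)
- Difference: d(n − b) / [n(n + d)], which is positive whenever d > 0 and b < n

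If deaths have no 1-year value, the >2 rate is therefore understated. If every death has a 6 at 1 year, the shortfall from deaths is zero.

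**3. Inputs for size.**

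- Subjects: 200, the maximum in SAP 3.
- Deaths, low: 3/191 = 1.6% neurological mortality in the prospective registry cited in Protocol 1.2.3; 200 × 3/191 = 3.1, taken as 3.
- Deaths, high: 30/793 = 3.8% neurological mortality in the retrospective study cited there; 200 × 30/793 = 7.6, taken as 8.
- Survivors with mRS >2: 8%, an assumption. The documents give no figure.
- Other missing scores: none, an assumption.

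**4. Size.** With survivor rate p and share of deaths m, the rate with deaths scored 6 is p + m(1 − p).

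- 3 deaths, m = 0.015: 0.08 + 0.015 × 0.92 = 9.4%, up 1.4 points
- 8 deaths, m = 0.04: 0.08 + 0.04 × 0.92 = 11.7%, up 3.7 points

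With whole-number counts and Clopper-Pearson 95% intervals:

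| Deaths | Deaths dropped | Deaths scored 6 |
|---|---|---|
| 3 | 16/197 = 8.1% (4.7 to 12.9) | 19/200 = 9.5% (5.8 to 14.4) |
| 8 | 15/192 = 7.8% (4.4 to 12.6) | 23/200 = 11.5% (7.4 to 16.8) |

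The shift, m(1 − p), depends little on the assumed survivor rate. At p = 3% it is 1.5 and 3.9 points; at p = 5% it is 1.4 and 3.8 points.

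**5. Effect of unscored survivors.** Take 8 deaths and 30% of the 192 survivors unscored, leaving 134 scored, 11 of them >2. Dropping deaths gives 11/134 = 8.2%. Scoring deaths as 6 gives 19/142 = 13.4%. If the unscored survivors resembled the scored ones, the rate in all 200 would be (192 × 11/134 + 8)/200 = 11.9%. The death rule alone then gives deaths too much weight, because every death counts but only some survivors do.

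**The case against.** The strongest reply is that the plan never excludes deaths. SAP 2 defines 6 as dead, so a 6 entered at 1 year counts as >2, and the schedule leaves room for optional and unscheduled entries. A reader might infer that the SAP specifies a survivor-only analysis. The text does not say so: what is missing is a derivation rule, and the bias depends on whether a 6 reaches the 1-year time point. That limits the claim but does not remove it, because nothing in the plan ensures that it does.

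Two other stronger readings also fail.

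- **A shortfall of about 2 to 5 points.** This comes from adding 3 to 8 deaths out of 200 to only 150 scored survivors, 12 of them >2: 12/150 = 8.0% becomes 15/153 = 9.8% or 20/158 = 12.7%. It mixes denominators and leaves 47 or 42 survivors unscored, a share with no source in the documents.
- **Unscored survivors also make the result look better.** The documents give no direction for that effect.

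It is also fair to say that mRS is not among the visible primary or secondary endpoints. Neurological death is in the primary safety endpoint, and SAP 7.9 reports death as an adjudicated event through 1 year, so deaths are not hidden. The total without a score can be read from the fixed population size. None of this corrects the mRS rate or its interval, and that total does not separate the dead from the unscored.

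**Conclusion.** The point holds as a gap in the derivation of the 1-year mRS. Unless a 6 is recorded at that time point, subjects who died leave the denominator and the >2 rate is too low. Under the stated assumptions the shortfall is 1.4 to 3.7 percentage points (8.0% against 9.4% to 11.7%).

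The size is illustrative. The two mortality figures count neurological deaths only. They come from studies with median follow-up of 6.6 and 19.3 months, and the study behind the higher figure included ruptured aneurysms. All-cause deaths by 1 year could be fewer or more. The 8% survivor rate and complete scoring of survivors are also assumptions.

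The primary endpoints are unaffected. The change is still worth making before analysis: it is cheap, and it brings the table into line with the SAP's own scale.

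**What to change.** In SAP 7.7 and 7.13.3, add that any subject who died from any cause by the 1-year time point is scored mRS 6 at 1 year and stays in the denominator. Take the death from the death/exit or adverse event record rather than the mRS form. Protocol 6 already collects all serious adverse events, which include those leading to death, so no new data are needed. Apply the same rule to the composite in Protocol 9.4 if it is reported.

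Beside the rate, show the number of survivors without a 1-year mRS, and state that their effect on the rate has unknown direction. Show separately any subjects whose vital status at 1 year is unknown, such as implant failures followed only to discharge. A bound counting every unscored survivor as >2 is not essential. With 150 scored survivors, 12 of them >2, and 8 deaths, it would be (12 + 8 + 42)/200 = 31%, which says little.

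The cost is one derivation rule and one or two table rows. The functional rate will look slightly less favourable. If many survivors are unscored, deaths will weigh somewhat too heavily, so the unscored count has to appear next to the rate.
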